Hypotheses: In comparison to NOK clients in the waitlist comparison group, NOK clients in the experimental group will experience improvements in (1) *positive body image* and (2) *positive self-image*, at posttest, follow-up 1, and follow-up 2.

3. What measurements and outcome measures (depended variables) are used?

- Body Appreciation Scale
- Physical Condition Subscale
- Body Areas Satisfaction Subscale
- Self-Objectification Questionnaire
- Body Responsiveness Scale
- Rosenberg Self-Esteem Scale
- Self-Kindness Subscale

NOK clients will also complete questions assessing their self-reported age, sex, height, and weight.

4. What is the statistical approach?

Statistical design:

- What are the independent and dependent variables?
- Is it a correlational or (quasi-)experimental design?
- Are human subjects randomly assigned to the conditions?
- For each independent variable, what design is used: within-groups or between-groups?

The study will take place entirely online, and comprises three writing exercises and four measurement points, spread over a period of 95 days.

• Day 1: Informed consent + Pretest (15 minutes) + Writing Exercise 1 (15 minutes)

- Day 3: Writing Exercise 2 (15 minutes)
- Day 5: Writing Exercise 3 (15 minutes) + Posttest (15 minutes)
- Day 12: Follow-up 1 (15 minutes)
- Day 95: Follow-up 2 (15 minutes)

We aim to test 100 female clients from the NOK: 50 clients will be randomised to the experimental group (intervention) and 50 clients will be randomised to the waitlist comparison group.

Clients in the experimental group will complete all aspects of the study, described above. Clients in the comparison group will only complete the assessments at pretest, posttest, and follow-ups. At the end of Follow-up 2, they can decide to receive the writing exercises.

5. How many subjects are measured based on a statistical power analysis?

We will need 82 clients. This is based on a power analysis with a (f = 0.25), $\alpha = 0.05$, and an 80% likelihood of detecting a true effect. We aim to test 100 clients to compensate for potential dropout.

6. Why should this study be done?

Improving body image is important because a negative body image is related to (further) weight gain, physical inactivity, unhealthy eating behaviour, negative mood, and low self-esteem. Positive body image is the most important predictor of weight loss and maintenance.

7. Is there any additional relevant information?

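### Is the sample size of 82 unsupported because Protocol III.4 and III.5 name no test, tested effect or correlation between measurements?

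*Protocol*

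**What the plan says.** Protocol III.5 gives the sample size: "We will need 82 clients. This is based on a power analysis with a (f = 0.25", with alpha 0.05 and "an 80% likelihood of detecting a true effect". The target is then raised to 100 to allow for dropout.

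Protocol III.4 carries the form's question "What is the statistical approach". The answer says that the study "comprises three writing exercises and four measurement points, spread over a period of 95 days". It adds randomisation of 50 clients to each arm and what each arm completes. It names no test.

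Protocol III.3 lists seven questionnaires or subscales as outcomes. The hypotheses in III.2 concern improvement relative to the waitlist group in body image and self-image "at posttest, follow-up 1, and follow-up 2". III.5 does not say which scale, time point or model effect the power figure refers to.

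**The concern.** The effect size f can describe several things in a design with two groups and four occasions: a group difference averaged over occasions, a group-by-time interaction, or a group difference at one occasion. At the same f, alpha and power these need very different numbers of clients, and most of them also depend on the correlation between occasions. A reader who has only the three stated inputs cannot rebuild 82 without adding something.

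If the basis is unknown, the 80% cannot be tied to a particular hypothesis in III.2. It would then be hard to say whether the trial had a fair chance of showing a difference on a given scale at a given time.

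**Working it through.** **Inputs from the protocol.** f = 0.25, so f² = 0.0625; alpha 0.05; power 80% (III.5). Two equal groups and m = 4 measurements (III.4).

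**Assumptions not in the protocol.** Equal correlation ρ between measurements, taken as 0.5 with a range of 0.3 to 0.7, and a two-sided (F) test. Each N is the smallest even total that reaches 80% by the noncentral F distribution with noncentrality λ.

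**Step 1: reproduce 82.** For the between-groups main effect over four measurements,

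λ = N f² m / (1 + (m − 1)ρ), with 1 and N − 2 degrees of freedom.

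- N = 82, ρ = 0.5: λ = 82 × 0.0625 × 4 / 2.5 = 8.2, power 0.808.
- N = 80, ρ = 0.5: λ = 80 × 0.0625 × 4 / 2.5 = 8.0, power 0.798.

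So 82 is exactly the smallest even number for this test. At ρ = 0.3 it would be 62 and at ρ = 0.7 it would be 100.

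**Step 2: other readings of f at the same alpha and power.**

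| Test | λ | N at ρ = 0.5 | N at ρ = 0.3 and 0.7 |
|---|---|---|---|
| Group-by-time interaction, m = 4 | N f² m / (1 − ρ) | 24 | 32 and 16 |
| Same, f taken from partial eta squared, m = 4 | f² (N − 2)(m − 1) | 62 | no ρ enters |
| Same, f taken from partial eta squared, m = 3 | f² (N − 2)(m − 1) | 82 | no ρ enters |
| Mean of three later points, unadjusted | 3 N f² / (1 + 2ρ) | 86 | 70 and 104 |
| One later point, adjusted for pretest | N f² / (1 − ρ²) | 98 | 118 and 68 |
| One later point, unadjusted | N f² | 128 | no ρ enters |

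The spread is real, but it is not a margin of error around 82. Each row gives f a different meaning and so assumes a different true effect. The last row also discards the pretest and two of the three later measurements.

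**Step 3: which reading fits the stated design.** Two rows give 82. The interaction route needs three measurements, whereas III.4 specifies four, and with four it gives 62. Of the calculations tried, only the between-groups main effect gives 82 with all four measurements at ρ = 0.5.

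**Step 4: what 82 offers for the hypothesised comparisons.** Suppose f = 0.25 stands for a difference of 0.5 SD at each later point. Then N f² = 82 × 0.0625 = 5.125.

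- Pretest-adjusted mean of the three later points: λ = 5.125 / v, with v = (1 + 2ρ)/3 − ρ². At ρ = 0.5, v = 0.667 − 0.25 = 0.417 and λ = 12.3, giving power 0.934. At ρ = 0.3 and 0.7 the power is 0.919 and 0.980.
- One pretest-adjusted later point: λ = 5.125 / (1 − ρ²), giving power 0.650, 0.733 and 0.879 at ρ = 0.3, 0.5 and 0.7.
- One unadjusted later point: λ = 5.125, power 0.609.

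Power at 82 therefore lies on both sides of 80%, depending on how the data are analysed.

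**Step 5: the margin to 100.** The allowance is 1 − 82/100 = 18%. If all 100 were retained, the main effect of Step 1 would have power 0.879 at ρ = 0.5 and 0.803 at ρ = 0.7.

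**The case for a change.** The strongest case for calling this a defect is that the protocol itself states a power result, so its basis belongs beside it and cannot be left to a later document. One sentence would suffice. Moreover, the calculation that best explains 82 averages the group difference over all four occasions, including a pretest taken before any writing exercise. That is not the hypothesised difference in improvement at the later points. A single later point has only 65% to 88% power after pretest adjustment, under the assumptions above.

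Part of this stands. The basis is not written down, ρ = 0.5 is an assumption, and the 80% should not be read as applying to every scale and time point.

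It does not carry further, for four reasons.

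- The sub-questions under III.4 ask about variables, type of design, random assignment and, in the form's words, "For each independent variable, what design is used: within-groups or between-groups". None asks for a named test.
- The test and the scale for the main comparison are matters that a statistical analysis plan commonly settles. None is at hand here, so their absence from the protocol is not evidence that they are undecided.
- An analysis that uses the pretest and pools the later points has well over 80% power at 82 when the correlations are equal. Power can be pushed down to 72% by letting later points correlate 0.8 with each other but only 0.3 with the pretest. Nothing in the protocol supports that pattern, and with 0.5 in place of 0.3 the same calculation gives 81%.
- A null result on one scale or time point will be judged mainly by its estimate and confidence interval, not by the planning figure.

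**Conclusion.** No change to the plan is needed. It is correct that f = 0.25, alpha 0.05 and 80% power do not by themselves determine 82, and that Protocol III.4 and III.5 leave out the test, the effect that f describes and the correlation. But 82 follows from a standard calculation using the protocol's own two groups and four measurements, at an assumed correlation of 0.5 (power 0.808). For that test the requirement runs from 62 to 100 over correlations of 0.3 to 0.7, and the recruitment target equals the upper end, though with no room for dropout there.

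Neither an error in the figure nor a shortfall in power has been shown. Recording the inputs would make the calculation easier to trace but would alter no number of clients, no visit and no analysis. The conclusion rests on equal correlations and two-sided testing, and on the main effect being the calculation intended, which the protocol does not confirm.

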The NOK declares that they would like to use this intervention with their clients, and has asked us to evaluate its effectiveness. The participants are clients who have undergone bariatric surgery approximately 6 months ago at the NOK. The NOK plans to use the present intervention to foster the (further) psychological well-being of its clients.

As described (page 3), we have already tested this intervention among a group of women with a negative body image. We will be using the same intervention material for the present research (see ethics application with approval number: ECP-137 13_02_2014).

The clients will complete the informed consent sheet online, at the beginning of the first session (Day 1, page 4).

8. What documents are enclosed in the application?

- □ Advertisement
- X Statement of consent of the external organisation where the study takes place
- X Information letter for subjects
- X Statement of consent form for subjects
- □ Cover story for subjects
- X Debriefing form for subjects

 Other documents, namely:.....

9. Only for adult subjects:

Participants are asked to be added to the test subject database (FPN-wide database with subjects who have previously indicated their willingness to participate in scientific research).

No

This concerns a database for and by FPN researchers, which is managed by the Research Support Department (RSD) of the FPN and contains details of subjects over the age of 18 years who are willing to participate in scientific research. The persons involved have expressly

given their consent. For more information visit:

www.maastrichtuniversity.nl/fpn/proefpersonen

IV Ethically Sensitive Aspects of the Study

Please explain below the method of dealing with ethically sensitive aspects of the planned study:

- 1. Please mark the relevant age and categories (multiple entries possible):
 - □ Students
 - X >17 years, with legal and mental capacity
 - <12 years</pre>
 - X Patients
 - □ 12-17 years, with legal and mental capacity
 - □ 12-17 years, without legal and mental capacity
 - □ >17 years with legal and mental capacity with cover story

2. How will informed consent be obtained and recorded? Please mark the relevant form(s)

Form 1

Forms
Form 1: For studies with persons of age and with legal and mental capacity, consent must be given by the person involved.

- Form 2: For studies with persons under the age of 12 years, consent must be given by at least one parent or guardian.

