 - Form 3: For studies with persons under the age of 18 years but over 11 years of age with legal and mental capacity, consent must be given by the child in addition to at least one parent or guardian.
- Form 3: For studies with persons (including children over 11 years of age) lacking legal and/or mental capacity, consent must be given by at least one parent or guardian or other (legal) representative.

Note: In case the absence of legal and/or mental capacity is temporary, renewed informed consent should be obtained from the subject directly once the capacity/capacities has/ve been re-established.

• Form 4: For studies with persons of age and with legal and mental capacity involving a cover story, consent must be given by the person involved.

3. What are the inclusion criteria?

Inclusion criteria: De NOK clients who are (1) women between 18 and 65 years old, (2) have undergone bariatric surgery approximately 6 months prior, and (3) qualify for NOK standard aftercare.

4. What are the specific exclusion criteria?

NA

5. Please describe in plain language what actions are required of the subjects or what behaviour will be observed:

Clients of the NOK (who meet the inclusion criteria) will receive information about the study from their treatment provider at the NOK, and can apply for the study via email. Clients can decide whether they would like to send us an email or not. If the client sends us an email, they will receive extended information about the study. Afterward they can decide themselves whether they would like to take part in the study or not. This decision has no consequences for the clients' further treatment at the NOK. If the client would like to take part in the study, she will be randomised to the intervention or comparison group. Afterward, the client will follow the research procedure (page 4). Clients may withdraw from the study at any moment, without needing to provide a reason. This also has no consequence for their treatment at the NOK.

- 6. What is the maximum load per subject per experiment? Please provide the following:
 - Maximum number of hours per session = 0.5
 - Maximum number of sessions per day = 1
 - Maximum number of days per experiment = 5
 - Total number of hours per participant per experiment = 1 hour and 45 minutes

7. Does the study include the use of equipment and measuring instruments?

No

8. Are there any risks of damage and discomfort involved for the participants of the study?

No

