9. Does the study involve video and audio recordings of subjects?

No

10. Are the subjects provided with all the information about the study beforehand?

Yes

11. Does the study involve deception?

Deception is when participants are not informed beforehand of the true nature of the study and what is expected of them. For research purposes, deception is vital to avoid socially desirable answers and demand characteristics, but it also goes against the principle of active, informed consent. In other words, it is a serious measure that should only be used if sufficiently motivated and surrounded with appropriate safeguards, including adequate debriefing after participation. Deception is not allowed in studies involving minors (< 18 years).

No

12. How much time are the subjects given to decide on participation?

Clients from the NOK who have undergone bariatric surgery approximately 6 months ago may take part in the study. Because we would like to keep this relatively consistent, clients will have approximately 2 weeks to decide whether they would like to take part or not.

13. What is the reward per participant per experiment:

Compensation per subject cannot be too great, as that would interfere with reasonable consideration and as such voluntary participation.

The FPN generally awards a maximum of EUR 7.50 per hour in cash or gift vouchers or (for students) 1 research participation credit with the possibility of a raffle for a predetermined gift amount at the end of the study among subjects who participated for the entire duration of the study. In case of a raffle, the content of the prize and chances of winning should be announced in advance.

In case of early termination of participation in the study, the participant will still receive the promised amount of compensation. If multiple compensations are used for repeated measurements, these will be awarded in proportion to the number of participations. Participation credits are registered via the Research Participation System (also called SONA) https://maastricht-fpn.sona-systems.com. Researchers (and students) need to comply with the rules and regulations of SONA.

X Compensation (maximum of EUR 7.50 per hour); for higher rates, please explain why:

Every client will receive 15 Euro (VVV gift voucher).

14. Are the subjects debriefed after their participation in the study?

- □ Yes, both in oral and written form (please provide written form with this application)

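### Clients are randomised before the Day 1 consent and pretest, with no statement of when they learn their arm; allocating after the pretest removes this pre-baseline risk at almost no cost

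*Protocol*

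**What the plan says.** Section IV.5 describes the client's path: she hears of the study from her treatment provider, sends an email, receives extended information and decides. Then: "If the client would like to take part in the study, she will be randomised to the intervention or comparison group". The next step is: "Afterward, the client will follow the research procedure (page 4".

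That procedure is the schedule in III.4, whose first entry is: "Day 1: Informed consent + Pretest (15 minutes) + Writing Exercise 1 (15 minutes". Section III.7 confirms when consent is recorded: "The clients will complete the informed consent sheet online, at the beginning of the first session (Day 1, page 4".

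On allocation, III.4 adds that "50 clients will be randomised to the experimental group (intervention) and 50 clients will be randomised to the waitlist comparison group", without placing randomisation in time. On the comparison arm it says: "Clients in the comparison group will only complete the assessments at pretest, posttest, and follow-ups". On leaving the study, IV.5 says: "Clients may withdraw from the study at any moment, without needing to provide a reason".

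**The concern.** Read together, these sections put randomisation before informed consent and before the baseline measurement. Nothing says that the arm is withheld until the pretest has been submitted, and the interval between allocation and Day 1 is not given.

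If clients learn their arm in that interval, two problems of unknown size and direction can follow.

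1. **Non-start that depends on arm.** A client who never opens the Day 1 session leaves neither consent nor pretest. She can be counted and her influence bounded in a sensitivity analysis, but her baseline is unknown. If this happens more in one arm, the clients who start are no longer the groups that were randomised.
2. **Pretest answers that depend on arm.** The seven outcome measures in III.4 are questionnaires or scales, and a waitlist cannot be masked once it is known. The pretest is the one assessment that could be kept free of knowledge of the arm. A distortion there carries into any change-score or baseline-adjusted analysis.

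This is a matter of trial conduct. No analysis plan can recover a pretest that was never completed, or undo answers given with the arm known.

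**Working it through.** **Order of steps, from the text**

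| Step | Source |
|---|---|
| 1. Client decides to take part | IV.5 |
| 2. Randomisation | IV.5 |
| 3. Day 1: online consent | III.4, III.7 |
| 4. Day 1: pretest | III.4 |
| 5. Day 1: Writing Exercise 1 (intervention arm only) | III.4 |

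No section gives another order, and disclosure of the arm appears nowhere.

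**The plan's own figure.** III.5 gives 82 clients for f = 0.25, α = 0.05 and 80% power. Take the between-groups effect of a repeated-measures ANOVA with 2 groups, m = 4 measurements and an assumed correlation ρ = 0.5 (the protocol gives none):

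λ = f²·N·m / (1 + (m − 1)ρ) = 0.0625 × 82 × 4 / 2.5 = 8.2, with 1 and 80 degrees of freedom: power 0.808.

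At N = 80, λ = 8.0 and power is 0.798, so 82 is reproduced. For two equal groups, f = 0.25 is a difference of 2f = 0.5 SD, the yardstick used below.

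**Risk 1: unequal non-start (rates assumed).** Suppose the fraction q of an arm with the lowest latent propensity to start is lost, and that propensity correlates r with body image. The mean propensity of those remaining rises by φ(z_q)/(1 − q):

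- q = 0.05: 0.1031 / 0.95 = 0.109
- q = 0.10: 0.1755 / 0.90 = 0.195
- q = 0.20: 0.2800 / 0.80 = 0.350

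Difference between arms = r × [shift(waitlist) − shift(intervention)], in SD:

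| Waitlist v intervention non-start | Difference in shift | r = 0.3 | r = 0.5 |
|---|---|---|---|
| 10% v 10% | 0 | 0 | 0 |
| 10% v 5% | 0.086 | 0.03 | 0.04 |
| 20% v 10% | 0.155 | 0.05 | 0.08 |
| 10% v 0% | 0.195 | 0.06 | 0.10 |
| 20% v 0% | 0.350 | 0.10 | 0.17 |

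Simulation with 50 per arm and 20,000 runs agrees for loss in one arm only: about 0.06 and 0.10 SD with 5 lost, 0.10 and 0.17 SD with 10 lost. These are unadjusted means; baseline adjustment removes the part carried by the pretest score. The sign depends on which arm loses more and on the sign of r, neither of which is known.

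**Risk 2: shifted pretest (shift assumed).** If knowing the arm moves pretest scores by s between arms and later scores are unaffected, a change score is biased by s and an ANCOVA with slope b by b·s, in absolute size. With b = 0.5:

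| s (SD) | Change score | ANCOVA |
|---|---|---|
| 0.05 | 0.05 | 0.025 |
| 0.10 | 0.10 | 0.05 |
| 0.30 | 0.30 | 0.15 |

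**Numbers and power.** The reserve for dropout is 100 − 82 = 18. If non-starters count towards the 100 and are not replaced, 5 of them leave 95 − 82 = 13 and 10 leave 90 − 82 = 8. Power is not the main issue: with 18% lost in one arm only (50 v 41), λ = 0.25 × (50 × 41/91) × 4/2.5 = 9.0, and power is still about 0.84 under the same model.

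**The case against.** The strongest reply has four parts.

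- **A lay summary is being read as a procedure.** IV.5 is a plain-language description, the order turns on one adverb, and the design section does not time the randomisation. Actual practice may be better than the text. That is possible, but IV.5 is the only statement of the order and nothing visible corrects it.
- **Agreement does precede allocation.** The client decides after receiving extended information, and IV.12 says "clients will have approximately 2 weeks to decide whether they would like to take part or not". This stands: she agrees informally before she is allocated. Together with the 15 Euro voucher for every client (IV.13) and later access to the exercises for the waitlist (III.4), it makes arm-related non-start less likely. It does nothing to protect the pretest answers, and recorded consent still comes after allocation.
- **Harm requires early disclosure, which no section states.** The information letter and consent form are listed as enclosures but are not in the text reviewed, and they might settle the point. This also stands, which is why the finding is a risk and not a demonstrated bias.
- **The sizes are assumed, and the reserve figures depend on a reading.** Equal non-start gives no bias, and the largest values need 20% loss in one arm and none in the other. III.4 speaks of testing 100 clients, which can be read as 100 who start; the reserve figures of 13 and 8 then fall away.

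Withholding the arm until the pretest is submitted would protect the pretest without moving randomisation. It would, however, leave allocation ahead of consent and would still allow randomised clients with no baseline.

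**Conclusion.** The concern holds. As written, allocation precedes both recorded consent and the baseline, and the protocol does not keep the arm from the client until the pretest is in. The order is certain from the text; the harm is conditional on clients learning their arm before Day 1.

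If they do, plausible assumptions put the non-start bias between 0 and about 0.17 SD on unadjusted means. An assumed pretest shift of 0.05 to 0.10 SD gives a bias of 0.05 to 0.10 SD in a change score, or 0.025 to 0.05 SD in an ANCOVA with slope 0.5; larger shifts scale in proportion. Set against 0.5 SD, these are modest but not negligible, and in either direction. The 82 clients required do not change. It should be fixed because avoiding it costs almost nothing. Reordering deals with the pre-baseline risk only: unmasked self-report at later assessments and dropout after allocation remain.

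**What to change.** Amend IV.5 and the III.4 schedule so that Day 1 runs as follows:

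1. online consent;
2. pretest completed and submitted;
3. automatic 1:1 allocation by the survey software, with the arm disclosed at that point;
4. Writing Exercise 1, for the intervention arm only.

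Define the randomised set as everyone allocated at step 3, and recruit until 100 clients have been allocated. A client who expresses interest but never starts is then never randomised, and every randomised client has a consent and a baseline.

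The cost is one reworded sentence in IV.5, one added step in the III.4 schedule and a randomiser element in the online survey, assuming the software in use supports it. Both arms already complete consent and pretest, so no extra sessions, staff or participants are needed.
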